7.4.1. Adverse events (AE)

AE DEFINITION

Adverse event means any untoward medical occurrence associated with the use of an intervention in humans, whether or not considered intervention-related. An AE can therefore be any unfavorable and unintended sign (including an abnormal laboratory finding), symptom, or disease temporally associated with the use of a medicinal (investigational) product, whether or not related to the medicinal (investigational) product.

NOTE 1- This includes any event that is a result of a use error or intentional misuse.

Subject: smART Plus Comparative Study Protocol - Beilinson

NOTE 2: This includes events related to the procedures involved (any procedure in the clinical investigation plan).

NOTE 3: For users or other persons this is restricted to events related to the investigational medical device.

AE CLASSIFICATION AND REPORTING

Group A- Interventional Device

All AEs will be recorded on the adverse events page of the eCRF. AEs will be recorded after the subject (or delegate) has signed the informed consent and throughout the study. Any medical condition that is present at the time that the participant is screened will be considered as baseline and not reported as an AE. However, if the study participant's condition deteriorates at any time during the study, it will be recorded as an AE. AE reporting and documentation will be discontinued, at the end of the study, immediately after feeding tube removal.

Information to be collected includes event description, time of onset, clinician's assessment of severity, relationship to study product (assessed only by those with the training and authority to make a diagnosis), and time of resolution/stabilization of the event. All AEs occurring during the study must be documented appropriately regardless of relationship. All AEs will be followed to adequate resolution.

Severity and relationship to study device will be assigned by the investigator as described below.

All adverse events will be graded for severity as follows:

- **Mild:** Events, sign or symptom, usually transient, requiring minimal or no special treatment and generally not interfering with participant's usual activities.
- **Moderate:** Events, sign or symptom, which may be ameliorated by simple therapeutic measures; yet, may interfere with usual activity.

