- **Severe:** Events, sign or symptom that are intense or debilitating and that interfere with usual activities. Recovery is usually aided by therapeutic measures.

All adverse events (AEs) must have their relationship to study intervention assessed by the clinician who examines and evaluates the participant based on temporal relationship and his/her clinical judgment. The degree of certainty about causality will be graded using the categories below.

- **Probably related:** Follows a reasonable temporal sequence from study device delivery/retrieval, and cannot be reasonably explained by known characteristics of the subject's clinical data or the surgical procedure applied.
- **Possible related:** Follows a reasonable temporal sequence from study device delivery/retrieval but could have been produced by the subject's clinical state or by the surgical procedures regardless of the study device.
- **Not related:** No relationship to study device activation is perceived.

Group B- Control Group

Subject: smART Plus Comparative Study Protocol - Beilinson

AEs recorded for group B should include only related or could affect (according to PI decision) the patient's medical condition that related to urine, feeding, GRV and REE.

7.4.2.Serious Adverse Events (SAE)

SAE DEFINITION

A "serious Adverse Event is an adverse event that:

- a) led to a death,
- b) led to a serious deterioration in health that either:
 - 1) resulted in a life-threatening illness or injury, or
 - 2) resulted in a permanent impairment of a body structure or a body function, or
 - 3) required in-patient hospitalization or prolongation of existing hospitalization, or
 - 4) resulted in medical or surgical intervention to prevent life threatening illness or injury or permanent impairment to a body structure or a body function.
- c) led to fetal distress, fetal death or a congenital abnormality or birth defect.

NOTE 1: This includes device deficiencies that might have led to a serious adverse event if a) suitable action had not been taken or b) intervention had not been made or c) if circumstances had been less fortunate. These are handled under the SAE reporting system.

NOTE 2: A planned hospitalization for pre-existing condition, or a procedure required by the Clinical Investigation Plan, without a serious deterioration in health, is not considered to be a serious adverse event.

SAE REPORTING

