- The two-sample T-test or Non-parametric Wilcoxon-Mann-Whitney Rank sum test for independent samples (as is appropriate) will be applied for testing the statistical significance of the difference in the estimated nursing time that was expended for GRV activities, and the amounts of GRV removed from the patient between the study groups.
- Convenience of use of the system and the user interface scores (by subjective staff questionnaire) will be summarized in an appropriate table by study group
- The two-sample T-test or Non-parametric Wilcoxon-Mann-Whitney Rank sum test for independent samples (as is appropriate) will be applied for testing the statistical significance of the difference in the assessment of urine flow monitoring related to patient condition and usability between the study groups.
- The two-sample T-test or Non-parametric Wilcoxon-Mann-Whitney Rank sum test for independent samples (as is appropriate) will be applied for testing the statistical significance of the difference in ICU length of stay (measured from admission to ICU until the decision to discharge is ordered) between the study groups.
- Chi-square test or Fisher's Exact test (as is appropriate) will be applied for testing the statistical significance of the difference in percent of subjects experiencing Ventilation associated events between the study groups.

9.2.5 Safety:

Adverse events will be coded using the Medical Dictionary for Regulatory Activities (MedDRA, most updated version) terminology and presented in tables by System Organ Class (SOC) and Preferred Term (PT).

Subject: smART Plus Comparative Study Protocol - Beilinson

AE data will be listed individually and summarized by SOC and by PT within a system organ class for each study group.

Frequency of TEAEs (Treatment-Emergent Adverse Events) and device-related adverse events will be summarized in tables by SOC, PT and study group and by seriousness.

Chi-square test or Fisher's Exact test (as is appropriate) will be applied for testing the statistical significance of the difference in percent of subjects experienced any AE, drug-related AE and SAE between the study groups.

Concomitant medications entered into the database will be coded using the World Health Organization (WHO) Drug Reference List, which employs the Anatomical Therapeutic Chemical classification system.

10. Regulatory, Ethical, and Study Oversight Considerations

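### Note 1 to the SAE definition takes in device deficiencies that harmed no one, and 9.2.5 tests SAE percentages between groups without saying whether those entries count

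*Combined protocol and SAP*

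**What the plan says.** - **SAE definition (7.4.2).** A "serious Adverse Event is an adverse event that" led to death, to serious deterioration in health, or to fetal harm (criteria a to c). Section 7.4.1 supplies the base term: "Adverse event means any untoward medical occurrence associated with the use of an intervention in humans".
- **Note 1 (7.4.2), still within the SAE definition.** "This includes device deficiencies that might have led to a serious adverse event if a) suitable action had not been taken", with two further hypotheticals (no intervention, less fortunate circumstances). It closes: "These are handled under the SAE reporting system".
- **Analysis (9.2.5).** Chi-square or Fisher's exact test is applied to the "difference in percent of subjects experienced any AE, drug-related AE and SAE between the study groups". No exclusion of Note 1 entries is stated. Section 9.2.1 makes all tests two-sided at 5%.
- **Recording (7.4.1).** For group A, "All AEs will be recorded on the adverse events page of the eCRF", whatever the relationship to the device. For the control arm, "AEs recorded for group B should include only related or could affect (according to PI decision"), limited to matters of urine, feeding, GRV and REE.
- **Devices.** Only group A receives the smART+ System (section 5). Group B is fed with the hospital's ordinary tubes and pumps (5.3.3).

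**The concern.** Note 1 describes near-misses: faults that could have caused serious harm but did not. An analyst who follows the SAE definition literally would count a patient with such a fault, and no harm, as a patient with an SAE. Group A's percentage would then combine injury with equipment failure, and the test in 9.2.5 would compare that mixture with a control percentage made up mainly of injury. Neither a significant nor a null result could be read as a statement about patient harm.

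An analyst who follows the opening words of the definition would leave the same patient out. Two competent analysts could therefore report different SAE rates from one database. The trial is open-label (5.1), so the choice could be made with allocation known. Safety is a listed secondary endpoint (2.2), so the counting rule should be fixed in advance.

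**Working it through.** **1. Do the passages agree?** They do not. The chain in 7.4.1 and 7.4.2 is: SAE, therefore AE, therefore an untoward medical occurrence. A deficiency with no medical occurrence fails at the last link, yet Note 1 says the SAE definition includes it. Section 9.2.5 does not settle the matter.

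**2. Where would the entries arise?** Note 1 speaks of device deficiencies without limiting them to the investigational device, so a hospital-pump fault in group B is not ruled out. Three features still point to group A:
- Only group A has the smART+ System.
- Its equipment logs data that the sponsor extracts directly (5.2.8); 5.3.5 lists no counterpart for group B.
- Group B recording is confined to events the PI judges relevant to the patient's medical condition, which a harmless fault would rarely be.

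Predominance in group A is therefore a sound inference, but it is not stated in the text.

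**3. How many entries would matter?** The plan gives no SAE rate, no deficiency rate and no power for this test, so there is no stated figure to reproduce. Inputs: 100 per arm (3.1), two-sided 5% (9.2.1). Assumptions: the same number of true SAE patients in each arm, and k further group A patients counted only for a harmless deficiency. Each adds 1/100 = 1 percentage point to group A.

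Fisher's exact two-sided p sums the hypergeometric probabilities no larger than that of the observed table. For 6 v 0:

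p = 2 × C(100,6)/C(200,6) = 2 × 0.01447 = 0.029.

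| Assumed SAE rate, both arms | Just short of p<0.05 | First p<0.05 | k needed |
|---|---|---|---|
| 0% | 5 v 0, p=0.059 | 6 v 0, p=0.029 | 6 |
| 10% | 20 v 10, p=0.073 | 21 v 10, p=0.049 | 11 |
| 30% | 44 v 30, p=0.057 | 45 v 30, p=0.041 | 15 |
| 50% | 64 v 50, p=0.063 | 65 v 50, p=0.045 | 15 |

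The uncorrected chi-square, which 9.2.5 also allows, is slightly less demanding. At 20 v 10, z = 0.10/√(0.15 × 0.85 × 2/100) = 1.98, p=0.048.

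**4. Chance of a false difference.** Let the true SAE rate be p in both arms, and let a share d of group A patients without a true SAE be counted for a harmless deficiency. The group A rate becomes p + (1−p)d; for p=10% and d=5% it is 0.10 + 0.90 × 0.05 = 14.5%. Exact enumeration of two binomials (n=100 each) with the uncorrected chi-square at 5% gives these rejection rates:

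| p | d=0 | d=2% | d=5% | d=10% | d=20% |
|---|---|---|---|---|---|
| 10% | 5.2% | 7.1% | 16.4% | 44.6% | 91.7% |
| 30% | 5.1% | 5.6% | 8.4% | 18.3% | 53.8% |
| 50% | 5.6% | 5.8% | 7.1% | 11.8% | 31.0% |
| 70% | 5.1% | 5.2% | 5.7% | 7.6% | 15.8% |

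All values of p and d are assumptions. As d grows, nearly all rejections fall against the device.

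**5. Does removing these entries suffice?** Set d=0, but suppose that 75% of group B's SAEs are recorded (an assumption), because an SAE is an AE and inherits the narrower control-arm rule. False rejection is then 9.8%, 22.4%, 44.4% and 72.6% at p = 10%, 30%, 50% and 70%. The test stays unreliable until recording is equal.

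**The case against.** The closing sentence of Note 1 can be read as a reporting route only: such deficiencies travel through the SAE system but are not SAEs for analysis. The opening words of the definition favour that reading, and 9.2.5 concerns adverse events coded in MedDRA. This stands in part. It shows that the text does not compel counting; it does not supply a rule against it, because the note also says the definition includes these entries.

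A reader might infer that such entries can occur only in group A, so that the comparison is biased by definition. The documents do not support that. Note 1 is not limited to smART+, whereas Note 3 to the AE definition names the investigational device when it means it. Control patients are also fed through devices that can fail. What can be shown is an unresolved counting rule with a likely tilt.

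The size may also be small. The scenario with no other SAEs is the least realistic, since the SAE reporting text in 7.4.2 expects a very large number of them. With d=2% and SAE rates of 30% to 70%, false rejection is 5.2% to 5.8%, close to nominal. Finally, this is a supporting test with no stated power or decision rule, and a tilt against the device would not manufacture a favourable safety claim. Both points limit the weight of the concern; neither removes the ambiguity.

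**Conclusion.** The concern holds as a conflict in the definition and a missing counting rule. Note 1 is worded to bring harmless deficiencies into the SAE class, the base definitions keep them out, and 9.2.5 tests the result without choosing. If they are counted and fall mainly in group A, the SAE comparison shifts against the device.

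The shift ranges from negligible (few such patients, common SAEs) to decisive (11 such patients per 100 at a 10% SAE rate). Where the trial would fall in that range cannot be said, because the documents give neither rate. The problem of interpretation does not depend on significance: a percentage that mixes faults with harm is not a measure of harm.

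The unequal recording rule is a separate defect, explicit in the text, that acts on the same test in the same direction. Resolving Note 1 alone would not make the comparison a fair statement about safety.

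**What to change.** 1. In 9.2.5, define the tested SAE variable as events meeting criteria a) to c) of 7.4.2.
2. List Note 1 deficiencies without a medical occurrence separately, by group: number of events, number of patients, component involved, and a 95% CI for the proportion of patients. Keep them outside the between-group test. Where a deficiency does accompany a medical occurrence, count that occurrence as an AE or SAE by its own outcome.
3. Add one eCRF flag that separates a deficiency without harm from an event with harm.
4. Leave the reporting of deficiencies unchanged.
5. As a separate change, apply the same AE and SAE recording rule in both groups.

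Items 1 to 4 cost a few sentences of analysis text and one data field, best added before further events are recorded. Item 5 means more data entry for control patients, and the SAE test should not be read as a safety comparison without it.

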7.4.3. Expected / anticipated adverse events

Expected/anticipated adverse events are AEs that are known to occur for the study intervention being studied and should be collected and recorded in the study eCRF (as other AEs).

Anticipated adverse events associated with the insertion and presence of feeding tubes include:

- Inconvenient sensation in the neck or chest during or after insertion of the feeding tube and during feeding.
- Nasal bleeding during insertion attempt of the tube.
- Difficulty in breathing, coughing and chest pain due to insertion of the tube, mistakenly, into the trachea.
- Difficulty in swallowing due to the presence of the feeding tube.
- Nausea and vomiting
- Pneumothorax

Anticipated adverse events associated with feeding are:

- Abdominal discomfort and pain
- Abdominal bloating
- Diarrhea

The study PI will be responsible for determining whether an adverse event (AE) is expected or unexpected. An AE will be considered unexpected if the nature, severity, or frequency of the event is not consistent with the risk information previously described for the study intervention.

 ART MEDICAL <small>PATIENT SAFETY TECHNOLOGY</small>	Number: CRO-C-2822	Date issued: 01-Mar-2021
	Rev.06	Page 29 of 35

Subject: smART Plus Comparative Study Protocol - Beilinson

Expected/anticipated adverse events will be reported in the study eCRF and marked as “Expected/anticipated adverse events”.

8. Monitoring Plan

Monitoring functions shall be performed in compliance with Good Clinical Practices, EN ISO 14155:2011, as outlined in 21CFR§821.43(d) and 21CFR§812.46, and according to any other local regulations.

ART MEDICAL will appoint a Clinical Monitor for this study. The Clinical Monitor should be qualified by training and experience to oversee the conduct of the study. The Clinical Monitor's responsibilities include maintaining regular contact with the investigational site, through telephone contact and on-site visits, to ensure that: 1) the study protocol is followed; 2) that complete, timely, and accurate data are gathered; 3) that problems with inconsistent and incomplete data are addressed; and 4) that complications and Unanticipated Adverse Device Effects are reported to the Sponsor.

The investigational site will provide to the monitor direct access to the trial related source data/documents, and reports for the purpose of monitoring and auditing by the sponsor, and inspection by local and regulatory authorities.

9. Statistical Considerations

9.1 Sample size consideration

Approximately 200 subjects will be enrolled for the complete multi-center comparative study (100 per group). An interim analysis will be performed after 100 subjects (50 in each group) are enrolled on the primary endpoint.

1- Based on the primary endpoint at interim analysis (feeding efficiency):

Sample size rationale:

The rationale for sample size calculation is based on a difference in feeding efficiency between the tested group (with smART+ System) and the current standard practice (group B).

Sample size justification:

The comparison between groups of food consumption estimations is reflected by Effect size, calculated as the difference between the groups normalized by the common standard deviation.

The calculation uses the following formulation: (Estimation in the tested group - Estimation in control group)/Common standard deviation Error! Bookmark not defined.Error! Bookmark not defined.

A sample size of 50 in each group will have 90% power to detect an **effect size of 0.70** using a two-group t-test with a 0.025 two-sided significance level. [1, 2]

A significance of 0.025 was used instead of the usual 0.05 (alpha adjustment) due to the increase in the chance of making a Type 1 error following two subsequent analysis.

2- Based on the secondary endpoints at end of study:

2.1 Ventilation days:

Sample size rationale:

Subject: smART Plus Comparative Study Protocol - Beilinson

The rationale for sample size calculation is based on a difference in Ventilation days between the tested group (with smART+ System) and the current standard practice (group B).

Sample size justification:

The comparison between groups in ventilation days is reflected by Effect size.

A sample size of 100 in each group will have 90% power to detect an **effect size of 0.46** using a two group t-test with a 0.05 two-sided significance level. [1, 2]

2.2 Ventilation Associated Events:
Sample size rationale:

The rationale for sample size calculation is based on a difference in the proportion of subjects with Ventilation-Associated Events between the tested group (with smART+ System) and the current standard practice (group B) of 20%.

Sample size justification:

A two group continuity corrected c^2 test with a 0.05 two-sided significance level will have 90% power to detect the difference between a Group 1 proportion, p_1 , and a Group 2 proportion, p_2 (**odds ratio of 2.70**) when the sample size in each group is 100.[3]

2.3 Length of stay:
Sample size rationale:

The rationale for sample size calculation is based on a difference in length of stay between the tested group (with smART+ System) and the current standard practice (group B).

Sample size justification:

The comparison between groups in ventilation days is reflected by Effect size.

A sample size of 100 in each group will have 90% power to detect an **effect size of 0.46** using a two group t-test with a 0.05 two-sided significance level. [1, 2]

References:

9.2 Endpoints analysis:
9.2.1 General:

All measured variables and derived parameters will be listed individually and, if appropriate, tabulated by descriptive statistics.

 ART MEDICAL PATIENT SAFETY TECHNOLOGY	Number: CRO-C-2822	Date issued: 01-Mar-2021
	Rev.06	Page 31 of 35

Subject: smART Plus Comparative Study Protocol - Beilinson

For categorical variables summary tables will be provided giving sample size, absolute and relative frequency and 95% CI (Confidence Interval) for proportions by study arm.

For continuous variables summary tables will be provided giving sample size, arithmetic mean, standard deviation, coefficient of variation (CV%), median, minimum and maximum and 95% CI (Confidence Interval) for means of variables by study arm.

All tests will be two-tailed, and a p value of 5% or less will be considered statistically significant.

The data will be analyzed using the SAS® version 9.4 (SAS Institute, Cary North Carolina).

9.2.2 Primary endpoint:

The two-sample T-test or Non-parametric Wilcoxon-Mann-Whitney Rank sum test for independent samples (as is appropriate) will be applied for testing the statistical significance of the difference in feeding efficiency between the study groups.

9.2.3 Secondary endpoints:

- The two-sample T-test or Non-parametric Wilcoxon-Mann-Whitney Rank sum test for independent samples (as is appropriate) will be applied for testing the statistical significance of the difference in number of ventilation days (Evaluated by the number of hours of etCO2 from the hospital electronic records) between the study groups.
- The two-sample T-test or Non-parametric Wilcoxon-Mann-Whitney Rank sum test for independent samples (as is appropriate) will be applied for testing the statistical significance of the difference in the estimated nursing time that was expended for GRV activities, and the amounts of GRV removed from the patient between the study groups.
- Convenience of use of the system and the user interface scores (by subjective staff questionnaire) will be summarized in an appropriate table by study group
- The two-sample T-test or Non-parametric Wilcoxon-Mann-Whitney Rank sum test for independent samples (as is appropriate) will be applied for testing the statistical significance of the difference in the assessment of urine flow monitoring related to patient condition and usability between the study groups.
- The two-sample T-test or Non-parametric Wilcoxon-Mann-Whitney Rank sum test for independent samples (as is appropriate) will be applied for testing the statistical significance of the difference in ICU length of stay (measured from admission to ICU until the decision to discharge is ordered) between the study groups.
- Chi-square test or Fisher's Exact test (as is appropriate) will be applied for testing the statistical significance of the difference in percent of subjects experiencing Ventilation associated events between the study groups.

9.2.5 Safety:

Adverse events will be coded using the Medical Dictionary for Regulatory Activities (MedDRA, most updated version) terminology and presented in tables by System Organ Class (SOC) and Preferred Term (PT).

Subject: smART Plus Comparative Study Protocol - Beilinson

AE data will be listed individually and summarized by SOC and by PT within a system organ class for each study group.

Frequency of TEAEs (Treatment-Emergent Adverse Events) and device-related adverse events will be summarized in tables by SOC, PT and study group and by seriousness.

Chi-square test or Fisher's Exact test (as is appropriate) will be applied for testing the statistical significance of the difference in percent of subjects experienced any AE, drug-related AE and SAE between the study groups.

Concomitant medications entered into the database will be coded using the World Health Organization (WHO) Drug Reference List, which employs the Anatomical Therapeutic Chemical classification system.

10. Regulatory, Ethical, and Study Oversight Considerations

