A two group continuity corrected c^2 test with a 0.05 two-sided significance level will have 90% power to detect the difference between a Group 1 proportion, p_1 , and a Group 2 proportion, p_2 (**odds ratio of 2.70**) when the sample size in each group is 100.[3]

2.3 Length of stay:

Sample size rationale:

The rationale for sample size calculation is based on a difference in length of stay between the tested group (with smART+ System) and the current standard practice (group B).

Sample size justification:

The comparison between groups in ventilation days is reflected by Effect size.

A sample size of 100 in each group will have 90% power to detect an **effect size of 0.46** using a two group t-test with a 0.05 two-sided significance level. [1, 2]

References:

9.2 Endpoints analysis:

9.2.1 General:

All measured variables and derived parameters will be listed individually and, if appropriate, tabulated by descriptive statistics.

 ART MEDICAL PATIENT SAFETY TECHNOLOGY	Number: CRO-C-2822	Date issued: 01-Mar-2021
	Rev.06	Page 31 of 35

Subject: smART Plus Comparative Study Protocol - Beilinson

For categorical variables summary tables will be provided giving sample size, absolute and relative frequency and 95% CI (Confidence Interval) for proportions by study arm.

For continuous variables summary tables will be provided giving sample size, arithmetic mean, standard deviation, coefficient of variation (CV%), median, minimum and maximum and 95% CI (Confidence Interval) for means of variables by study arm.

All tests will be two-tailed, and a p value of 5% or less will be considered statistically significant.

The data will be analyzed using the SAS® version 9.4 (SAS Institute, Cary North Carolina).

9.2.2 Primary endpoint:

The two-sample T-test or Non-parametric Wilcoxon-Mann-Whitney Rank sum test for independent samples (as is appropriate) will be applied for testing the statistical significance of the difference in feeding efficiency between the study groups.

9.2.3 Secondary endpoints:

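### The sample size item for ventilator-associated events gives a 20% figure, an odds ratio of 2.70, 100 per group and 90% power that cannot all hold, and p1 and p2 have no values

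*Combined protocol and SAP*

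**What the plan says.** Section 9.1 gives three secondary-endpoint calculations for the full 100 per group; item 2.2 is the one for VAE.

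- **Rationale.** It rests on a "difference in the proportion of subjects with Ventilation-Associated Events between the tested group" and the "current standard practice (group B) of 20" per cent.
- **Test.** "A two group continuity corrected c^2 test with a 0.05 two-sided significance level".
- **Claim.** The test at the 0.05 "two-sided significance level will have 90% power to detect the difference between a Group 1 proportion" and a Group 2 proportion, with an "odds ratio of 2.70" and 100 per group. The two proportions appear only as the symbols p1 and p2.
- **Planned analysis.** Section 9.2.3 applies a chi-square or Fisher's exact test to the "difference in percent of subjects experiencing Ventilation associated events between the study groups". It names no continuity correction.

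The combined document contains the item twice, with the same figures both times. No VAE rate is given anywhere else.

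**The concern.** An odds ratio fixes the power of a two-proportion test only together with a base rate. Item 2.2 gives no base rate, unless the 20% is meant to be one. The sentence attaches the 20% most naturally to the absolute difference, but its wording also allows the group B rate. If the 20% conflicts with the other figures on each of these readings, a reader cannot tell which VAE rates or which effect the trial is powered for, and the stated 90% is not supported. A non-significant VAE result would then be hard to interpret.

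**Working it through.** **Inputs, all from section 9.1 item 2.2 unless noted:** two-sided alpha 0.05 (z = 1.960); power 90% (z = 1.2816); odds ratio (OR) 2.70; n = 100 per group; 1:1 allocation (section 5.1); continuity-corrected chi-square test; a figure of 20% whose meaning is unclear. All paired rates below are back-solved from these figures and are not in the documents.

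**Formulas.** Let d = |p1 − p2|, p̄ = (p1 + p2)/2, A = √[2p̄(1 − p̄)] and B = √[p1(1 − p1) + p2(1 − p2)].

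- Uncorrected size per group: n′ = (1.960·A + 1.2816·B)² / d²
- Corrected size per group: n = (n′/4)·[1 + √(1 + 4/(n′d))]²
- Corrected power at n: m = (nd − 1)²/(nd²), then power = Φ[(d√m − 1.960·A)/B]
- Higher rate from lower rate p: 2.70p/(1 + 1.70p)

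**Step 1. Does the stated claim reproduce without the 20%?** Yes, for some base rates. At 28% vs 51.2% power is 90.1% and the required n is 100. At 49% vs 72.2% power is again 90.1%. Over all base rates, OR 2.70 reaches 90% power at 100 per group when the lower rate is between 27.6% and 49.3%. The difference is then 23.1 to 24.3 points.

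**Step 2. 20% as the absolute difference.** Setting 2.70p/(1 + 1.70p) − p = 0.20 gives 1.7p² − 1.36p + 0.20 = 0, so p = (1.36 ± √0.4896)/3.4 = 0.194 or 0.606. The pairs are 19.4% vs 39.4% and its mirror, 60.6% vs 80.6%. For both, A = 0.6444 and B = 0.6287.

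- m = (20 − 1)²/(100 × 0.04) = 361/4 = 90.25
- Power = Φ[(0.20 × 9.5 − 1.960 × 0.6444)/0.6287] = Φ(1.013) = 84.4%
- n′ = (1.2630 + 0.8057)²/0.04 = 107.0, so n = (107.0/4)·[1 + √(1 + 4/21.4)]² = 116.8, that is 117 per group

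**Step 3. The other readings, by the same formulas.**

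| Meaning of 20% (OR 2.70) | Rates | Power at 100, corrected | Power at 100, uncorrected | n per group for 90%, corrected |
|---|---|---|---|---|
| Absolute difference | 19.4% vs 39.4% | 84.4% | 87.9% | 117 |
| Lower rate | 20% vs 40.3% | 85.1% | 88.4% | 115 |
| Control rate, reduced by device | 20% vs 8.5% | 56.8% | 64.7% | 209 |
| Relative difference | 85.3% vs 68.2% | 77% | 82% | 139 |

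Exact enumeration of the corrected test for the first three rows gives 84.9%, 85.5% and 56.8%, so the approximation is not the cause.

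**Step 4. The reverse check.** Hold the difference at 20 points with 90% power and 100 per group. The lower rate must then be at most 12.8%, or at least 67.2% in the mirror case, and the OR is at least 3.33. For example, 12.5% vs 32.5% gives 90.2% power with OR 3.37. So OR 2.70 at 90% power requires 23.1 to 24.3 points, while 20 points at 90% power requires an OR of 3.33 or more. The two sets of figures do not meet.

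**Step 5. Without the continuity correction.** OR 2.70 at 90% power still needs a difference of at least 21.3 points, and a 20-point difference still needs an OR of at least 2.92.

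**The case against.** The sentence that makes the power claim does not contain the 20%. Taken alone it is coherent, as step 1 shows, so the fault may be one loosely worded or rounded figure in the rationale plus an omission of p1 and p2. On the likelier readings the shortfall is only 5 to 6 power points. It is about 2 points if the final chi-square test is run uncorrected, which section 9.2.3 leaves open. The 57% depends on taking 20% as the group B rate, which is not the most natural reading. VAE is secondary, and neither the analysis nor enrolment would change.

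Much of this stands: the conflict arises only once the 20% is added, the gap is modest on the most natural reading, and the 57% is conditional. It cannot be excluded, though, because the declared endpoint is a reduction in VAE.

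The objection does not reconcile the figures. The 20% is given as the basis of the calculation. A difference of 23 to 24 points does not round to 20, and 3.33 does not round to 2.70. Dropping the correction does not close the gap, and item 2.2 names the correction. A one-sided 0.05 test would give 90.9% and 91.3% on the first two readings, but item 2.2 says two-sided and section 9.2.1 makes all tests two-tailed. If the 20% is set aside, the 90% cannot be checked, because no base rate remains.

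**Conclusion.** The concern holds. Under the named test, none of the four readings of the 20% is compatible with OR 2.70, 100 per group and 90% power together. If the 20% and the OR are both kept, power is about 84% on the most natural reading, 85% with 20% as the lower rate, 77% as a relative difference and 57% as a control rate that the device reduces. The documents do not show whether the 20%, the OR or the power is the wrong figure.

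The result rests on the two-sided 0.05 level, the continuity correction and equal groups, all as stated in the plan. It concerns the stated power of one secondary endpoint. It should be corrected, but it does not bear on the primary-endpoint calculation.

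**What to change.** In section 9.1 item 2.2, in both places where it appears, the sponsor should state p1 and p2 by group, the basis for them, and what the 20% denotes. The item should then give the power, or the odds ratio detectable with 90% power, at 100 per group for those values. Depending on which figures the sponsor keeps:

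- **20-point difference and OR 2.70:** state about 84% power.
- **OR 2.70 and 90% power:** replace 20% by a difference of about 23 to 24 points, with a lower rate of about 28% to 49%.
- **20-point difference and 90% power:** replace OR 2.70 by an OR of at least about 3.33, with a lower rate of at most about 12.8% (or at least about 67.2%).

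Section 9.2.3 should also say whether the chi-square test is continuity corrected, so that the analysis matches the test used for sizing.

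The cost is rewording one paragraph in its two copies and adding a few words to section 9.2.3. One stated figure becomes less favourable: either lower power or a larger detectable effect. Enrolment does not change.
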